## **8.0 PROTECTION OF HUMAN PARTICIPANTS**

The protocol for this study will meet approval by the University of Michigan Institutional Review Board prior to initiating any of the described study activities.

### D 1. Human Participants Involvement And Characteristics Removing Participants From The Protocol.

Respondents who meet eligibility criteria will be invited to participate in the baseline screening assessment. While we have chosen the above eligibility criteria based on previous work, we will make adjustments to the future, larger trial, based on the results and feedback from our proposed pilot.

### D 2. Sources Of Materials

For Phase II (intervention), data will be collected through the following methods: finger stick capillary blood samples, blood pressure measurements, weight, and height. Data that are obtained specifically for research purposes will be collected only with informed consent. All data will be collected over the course of the award period.

### D 3. Potential Risks

Participation in this study involves minimal foreseeable risks. Participants will be asked to provide finger stick capillary blood samples during assessments. Risks associated with finger stick capillary blood draws include: minor discomfort from obtaining the blood sample, minor pain, bruising, or bleeding at the puncture site similar to any other routine blood sample collections. With self-report surveys, there is also the small risk that prompting patients to review their diabetes care practices and providing them with feedback about their diabetes-related health outcomes (e.g., A1C, blood pressure) could cause some emotional discomfort or anxiety. Such discomfort would likely prime patients and their primary care physician or group facilitator to address any problems identified. Other risks include breach of confidentiality of study data.

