We propose to develop training for our male peer leaders to specifically encourage conversations regarding beliefs that affect men's health and to allow modeling of alternative views and perspectives that allow for successful disease management to be framed as competence and strength. Given that the life expectancy for Black men in the US is 71, we hypothesize that targeting men in earlier stages of T2D will assist greatly in facilitating healthy aging and improving diabetes-related health outcomes later in life.

Based on our previous work, the ***long-term goal*** of our research is to determine the most effective, practical, and sustainable approach to provide diabetes self-management education and support (DSMES) to older Black men. The ***objective*** of this proposal is to examine the relative effectiveness, feasibility, and acceptability of a peer-leader intervention for Black men with T2D. To accomplish this objective, we will engage in a developmental phase and a validation phase [pilot randomized control trial (RCT)]. The RCT will be conducted with N=60 Black adult residents of metro Detroit, MI. Participants will be randomized to an enhanced usual care group or the tailored peer-leader diabetes self-management support group (PLDSMS). We ***hypothesize*** that 1)

participants in the PLDSMS group will have improved outcomes over the control group, and 2) an evaluation of measures will confirm efficacy of the intervention. Measures will be collected at baseline, 3-months and a 3-month follow-up. The primary outcome will be change in self-management behaviors measured through completion of the Perceived Diabetes Self-Management Scale and a self-report questionnaire measuring a broad range of diabetes self-management behaviors post intervention and at 3-month follow up. Secondary outcomes will be change in A1c, weight, blood pressure, quality of life, diabetes related-distress, diabetes social support, and adherence to gender norms. We **hypothesize** that 1) participants in the PLDSMS group will have improved outcomes over the control group, and that 2) participants in the PLDSMS will achieve DSMES skills at significantly higher levels than participants in the control group.

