### **4.0 Participants and Recruitment**

*Participants will be 64 Black/African American men ages 55 years or older and meet the inclusion criteria listed below. During the Phase II pilot we will individually randomize each participant with a 50/50 randomization scheme to either the peer led DSMS or a control group. Four of the participants will attend 30- hours of training and function as peer leaders during the intervention DSMES.*

**Inclusion:** Inclusion criteria for the Phase II (intervention) will include males age 55 or older who are Black/African American, and who've had diagnosis of T2D for a six-month duration or longer.

**Exclusion:** Exclusion criteria for Phase II will include: non-ambulatory, serious health conditions (morbid obesity and severe symptomatic heart disease, visual impairment, renal failure, and peripheral neuropathy), psychiatric illness (severity requiring hospitalization) or cognitive deficit (illness determined using the Montreal Cognitive Assessment tool) and serious diabetes complications (e.g. blindness) that would impede meaningful participation. We considered restricting eligibility to a higher-risk population of participants with  $A1c \geq 8\%$ . Preliminary data suggest that over 50% of the proposed study sample will have an  $A1c \geq 8\%$ . Focusing on all older Black men with T2D allows us to cast a wide net for secondary prevention and public health impact. Persons who meet eligibility criteria will be invited to participate in the baseline screening assessment. While we have chosen the above eligibility criteria based on previous work, we will make adjustments to the future, larger trial, based on results and feedback from our proposed pilot.

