## **7.0 MEASURES**

### **Primary Outcome Measures**

Regimen adherence will be measured using the Perceived Diabetes Self-Management Scale, a self-report questionnaire used to measure a broad range of management behaviors, such as insulin management, dietary management, blood glucose monitoring, symptom response, and parent assistance/supervision.

Metabolic Control will be measured via hemoglobin A1c (HbA1c). HbA1c will be collected using the DCA 2000 point-of-care testing instrument.

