### **9. DATA AND SAFETY MONITORING PLAN**

**Adverse Events:** The PI will monitor adverse events throughout the clinical trial period. To ensure staff participation in data safety and monitoring activities, all members of the project team (research assistants and staff) will be trained on the specifics of the data safety and monitoring plan. Field staff will be trained on what constitutes an adverse event to a participant and instructed to report any adverse events immediately to the principal investigator, [name].

For the purposes of this study, adverse events will be considered any undesirable sign, symptom, or medical condition occurring during the study, whether or not related to the intervention. Adverse events include new events not present during the training period or events that were present during the training period but increased in severity over time. Each adverse event will be recorded and assessed for its date of onset, duration, severity, seriousness, and relationship to study treatment, and any action/treatment that is required. All adverse events will be collected, analyzed, and monitored using an adverse event form. Furthermore, the committee will establish “alert” values for A1C and blood pressure. The PI will notify the subject and the subject’s physician whenever there are laboratory results above these values because of the clinical implications of a value substantially out of normal range.

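### Hypoglycaemia is not named as a risk, a T0/T1 measure or a prompted adverse event, so an HbA1c change cannot be set systematically beside low-glucose events by arm

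*Combined protocol and SAP*

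**What the plan says.** **Outcome.** Section 7.0 lists HbA1c under primary outcome measures, and the Specific Aim 2 analysis models it as one. Sections 1.0 and 2.0 place it among the secondary outcomes, but the point does not depend on which is meant. Section 2.0 hypothesises that "participants in the PLDSMS group will have improved outcomes over the control group". That lower HbA1c counts as better is implied, not written as a rule.

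**Who may enrol.** Section 4.0 has no criterion on insulin or other glucose-lowering treatment. A restriction to A1c of 8% or more was considered and not adopted: "Focusing on all older Black men with T2D allows us to cast a wide net". Section 7.0 describes the self-management scale as covering behaviours "such as insulin management, dietary management, blood glucose monitoring, symptom response".

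**Risks.** D 3 begins "Participation in this study involves minimal foreseeable risks". It then names finger-stick effects, emotional discomfort from surveys and feedback, and loss of confidentiality. Of the emotional discomfort it says "Such discomfort would likely prime patients and their primary care physician or group facilitator to address any problems identified". Neither hypoglycaemia nor any equivalent term appears in the document.

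**Measures.** The named T0 and T1 measures (Sections 5.0 and 7.0) are height, weight, blood pressure, HbA1c, self-management, gender norms, social support, distress and quality of life. Further questionnaires, including one on use of health services, are mentioned without their items.

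**Adverse events.** Under Section 9, "adverse events will be considered any undesirable sign, symptom, or medical condition occurring during the study", whether or not related to the intervention. Events go on a form with onset, severity, seriousness and relationship. Serious events are collected and adjudicated, and the monitoring board reviews interim safety data. The section gives no list of events to ask about and no tabulation by arm.

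**The concern.** The plan intends to estimate an effect on HbA1c in a population that may include insulin users and men who start at a low HbA1c. In such men low glucose is a foreseeable event, and a reader of the results will want to see it next to the HbA1c change. As written, an episode enters the data only if someone reports it or it is serious enough to be noticed. One managed at home need not be recorded.

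Two things are at stake. First, the HbA1c result would have no systematic by-arm count of low-glucose events beside it. Second, any count that did emerge could differ between arms because one arm had more opportunities to report. A missing definition can be supplied before analysis. An event that was not asked about at T0 and T1 cannot be recovered afterwards.

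**Working it through.** There is no plan figure for hypoglycaemia to reproduce. The check is mainly of the text, with some arithmetic for scale.

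**1. Every route by which an episode could be recorded**

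| Route | Where | Would it capture an episode? |
|---|---|---|
| Named risk | D 3 | Not named |
| T0/T1 biometrics | 5.0, Baseline Assessment | No such measure |
| Self-management scale | 7.0 | Symptom response is a behaviour, not a count of events |
| Unspecified questionnaires | 7.0 | Possibly, if the episode led to use of care |
| Adverse event form | 9 | Yes, if volunteered or noticed; no prompt specified |
| Serious events | 9 | Yes, if serious |
| Alert values | 9 | No; they concern A1C and blood pressure results above a limit |

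**2. Opportunity to volunteer an episode** (Section 5.0, Intervention and Control Group)

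- Intervention: 6 education + 6 support = 12 planned sessions.
- Control: 6 education sessions, no support sessions.
- Ratio: 12 / 6 = 2.

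Section 1.0 puts the support sessions in weeks 9 to 14. If the control classes also run in weeks 3 to 8 (an assumption; their timing is not stated separately), control men have no planned session in the six weeks before the T1 window. The T0 and T1 assessments are the contacts that both arms share, and no hypoglycaemia question is specified there.

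**3. Number available for a by-arm count** (Section 7.0, Power Analysis)

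- 60 × (1 − 0.20) = 48, which matches the plan's expected final sample.
- 48 / 2 = 24 per arm, assuming an equal split.

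**4. What prompted data could and could not show**

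The event rates here are assumptions; the documents give none.

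- Chance of at least one man with an episode in an arm of 24, 1 − (1 − p)^24: for p = 0.05, 1 − 0.95^24 = 0.71; for p = 0.10, 1 − 0.90^24 = 0.92.
- One-sided 95% upper limit if none of n men reports an episode, 1 − 0.05^(1/n): for n = 24, 11.7%; for n = 30, 9.5%.
- Approximate power to compare arms, two-sided 5%, 24 per arm, using Φ[(|p₂ − p₁| − 1.96·√(2p̄(1−p̄)/n)) / √((p₁(1−p₁) + p₂(1−p₂))/n)]:
  - 10% vs 20%: (0.10 − 1.96 × 0.1031) / 0.1021 = −1.00, power 0.16.
  - 10% vs 30%: (0.20 − 1.96 × 0.1155) / 0.1118 = −0.24, power 0.41.

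A standard question would therefore give each arm a proportion with an interval, but no useful test between arms. These figures describe what the added items would yield. They do not measure a defect in the present plan.

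**The case against.** The strongest reply is that Section 9 already covers the event. Its definition takes in any untoward symptom, related or not, and each event is to be recorded, analysed and monitored. Serious events are adjudicated, and the monitoring board sees interim safety data. This is a 60-man behavioural pilot in which the study supplies no drug and sets no glucose target. Both arms receive the education classes, so the randomised difference is peer involvement and support. Much of this stands, and it rules out several stronger readings that a reader might infer:

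- *That an HbA1c gain cannot be weighed against low glucose at all.* Volunteered and serious episodes would be captured. What is not assured is systematic capture that is comparable between arms.
- *That nobody asks.* The adverse event form and some questionnaires are not reproduced. The documents support only that no such question is specified.
- *That hypoglycaemia is the main harm.* The documents give no rate, no share of men on insulin and no ranking of harms.
- *That the intervention aims to change insulin use.* Insulin appears in a description of what a questionnaire covers: "such as insulin management, dietary management, blood glucose monitoring, symptom response, and parent assistance/supervision". The mention of parents suggests the wording was carried over from a paediatric study. It is weak evidence of intervention content.
- *That D 3 plans for physicians to intensify treatment.* The sentence on addressing problems describes how emotional discomfort might resolve.

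The reply does not remove the twofold difference in planned sessions or the absence of a by-arm tabulation. Nor does it explain why hypoglycaemia is missing from the risk list when insulin users may enrol.

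**Conclusion.** The point holds in a limited form. HbA1c is an outcome of main interest and insulin users may enrol at any HbA1c. Hypoglycaemia is nevertheless not a listed risk, a named T0/T1 measure or a specified prompted event. With 12 planned sessions against 6, unprompted reporting is not assured to be equal between arms. The direction and size of any imbalance cannot be worked out from the documents.

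This rests on two assumptions: that some enrolled men use treatment that can cause low glucose, which the criteria permit but do not quantify, and that the unseen forms contain no standard question. If the adverse event form or a questionnaire already asks about hypoglycaemia identically in both arms, the remaining work is to say so, tabulate it and add it to D 3.

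The plan does not contradict itself here and no planned estimate is made invalid. It is a low-cost improvement worth considering.

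**What to change.** 1. Add two fixed recall items to the T0 and T1 questionnaire, worded identically in both arms and with the same recall window: any symptomatic low-glucose episode, and any episode needing another person's help. The T0 answer separates earlier episodes from new ones.
2. Report, by arm and time point, the number of randomised men with at least one episode over the number asked, with an exact 95% interval, beside the HbA1c result. Label the table descriptive and make no between-arm test.
3. Name hypoglycaemia among the risks in D 3.
4. Keep the Section 9 adverse event reporting as it is; the recall items supplement it.

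The cost is two questions in a baseline assessment of about two hours and in its T1 repeat (my estimate is about a minute of participant time), one sentence in D 3 and one table. Recall is imperfect, but it would be sought in the same way in both arms. No change to treatment is proposed.

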### Protection Against Risk

All questionnaires and instrumentations are standardized measures that have been used in our own trials and in other diabetes research and there are no significant risks anticipated related to the completion of them. However, breaks will be given as needed to reduce fatigue, or measures read to adolescents, and research assistants will be appropriately trained to obtain personal information in a sensitive fashion. Research staff will be trained in research ethics, confidentiality protection, and HIPAA prior to and throughout the study period. All peer leaders must pass standardized training prior to providing service to participants and will also be trained in protection of participant confidentiality.

At the time of study enrollment, participants will be assigned a study identification number to be used in all study materials and data for the duration of the study. All identifying information will be separated from the data and laboratory values. A master list that contains participants names and study identification number will be kept in a locked filing cabinet in the School of Social Work. Audio/visual recordings of the intervention for fidelity purposes will also be stored securely on a password protected computer only accessible to study personnel and will be destroyed upon study completion. The principal investigator ([name]) and the research assistant will be the only persons who have access to the file linking study ID# to each subject. Participants will be assured that all data they provide to the study will be confidential, unless it is necessary to "alert" both the patient and their physician because of a laboratory value outside of the normal ranges that reflects a risk requiring immediate attention. Participant's physicians will receive a report of participant laboratory values after each assessment. All reports will use aggregate data. Subject names or other identifiers will not be reported. No persons from the senior center, Ypsilanti Seventh Day Adventist Church, or other community based location will handle or have access to personal health information or participant survey data.

#### D 6. Potential Benefits Of The Proposed Research To The Participant And Others

Participants will have the potential to benefit from the study by receiving free diabetes self-management education and support from the intervention and also an opportunity to discuss barriers and facilitators to recruitment and retention of men and women in a large-scale intervention. There are also benefits to society from the research through its potential to improve diabetes self-management interventions for persons with Type 2 diabetes. We feel the benefits of participating in this study significantly outweigh the risks.

### **9. DATA AND SAFETY MONITORING PLAN**

**Adverse Events:** The PI will monitor adverse events throughout the clinical trial period. To ensure staff participation in data safety and monitoring activities, all members of the project team (research assistants and staff) will be trained on the specifics of the data safety and monitoring plan. Field staff will be trained on what constitutes an adverse event to a participant and instructed to report any adverse events immediately to the principal investigator, [name].

For the purposes of this study, adverse events will be considered any undesirable sign, symptom, or medical condition occurring during the study, whether or not related to the intervention. Adverse events include new events not present during the training period or events that were present during the training period but increased in severity over time. Each adverse event will be recorded and assessed for its date of onset, duration, severity, seriousness, and relationship to study treatment, and any action/treatment that is required. All adverse events will be collected, analyzed, and monitored using an adverse event form. Furthermore, the committee will establish “alert” values for A1C and blood pressure. The PI will notify the subject and the subject’s physician whenever there are laboratory results above these values because of the clinical implications of a value substantially out of normal range.

All serious medical events will be reported within one business day of their identification. All serious, fatal or life-threatening adverse events will be reported to UM IRB and the NIH within 24 hours of its identification. All causes of death are considered to be serious medical events. Unexpected moderate or severe adverse events will be reported in writing to the IRB and NIH. Serious medical events will be collected throughout the intervention phase of the study. The PI, along with the study physician, [name], and/or co-Investigator [name], will adjudicate whether or not each serious adverse event may be attributable to study participation. Events that involve an unexpected adverse event and are possibly or probably related to participation in the study will be reported to the IRB at University of Michigan within one business day. Annual reporting of aggregate adverse events to the IRB and NIH will be performed. All research project personnel will complete training in the protection of human research participants. The PI and research assistant will verify appropriate reporting of adverse events, quality of data collection, and adherence to the study protocol. Participant dropout rate will also be monitored and reviewed for needs or trends based on specific participant characteristics.

**Data Safety & Monitoring Board:** The DSMB will hold a minimum of two conference calls over the award period (approximately two hours per call) to discuss the progress of the intervention and review research results, if applicable. At the first meeting, the board will elect a chair of the DSMB. To facilitate these conference calls, the principal investigator will prepare a report on the progress of the project to date. This report will be circulated well in advance of the conference call to allow all members ample time to read it. These calls will be scheduled and organized by the study coordinator and will be held at a time convenient for all members.

The DSMB is responsible for assuring that study participants are not exposed to unnecessary or unreasonable risks and that the study is being conducted according to high scientific and ethical standards. Specifically, the DSMB will:

1. Assess the performance of the study with respect to subject recruitment, retention and follow-up, protocol adherence, and data quality and completeness, in order to ensure the likelihood of successful and timely milestone completion.

2. Monitor interim data regarding the safety of the study, including adverse events. The DSMB may, at its discretion, examine effectiveness data as well.
3. Review abstract and publications of main findings prior to submission to ensure the study is being reported appropriately.
4. Review and consider any protocol modifications or ancillary studies proposed by the study investigators after the main study begins to ensure that these do not negatively impact on the main trial.
5. Advise the NIA and the study investigators as to whether a protocol should continue as scheduled or undergo a modification due to a finding from the monitoring process.
6. Make recommendations to the NIDDK and principal investigator concerning continuation or conclusion of the trial.

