**Control Group (Control n=30)** Participants randomized to the control group will receive 6 sessions of group-delivered DSME provided by a CDCES; however they will not receive any DSMS or ongoing support from PLs and the PL will not participate in the DSME sessions. Based on several years of experience in Detroit, providing all participants with DSME and educational materials minimizes ethical concerns regarding assignment of underserved populations to receive a no-treatment control. To ensure treatment fidelity, three DSMS sessions will be selected at random and recorded and rated for fidelity by our research team.

**Peer Leaders (n=4)** Participants recruited to be PLs for the intervention group will attend PL training (described below), co-facilitate DSME sessions with a CDCES, lead DSMS sessions, and complete the same battery of assessments as all other participants in the study.

**Peer Leader Training:** The peer leader training curriculum will be based on materials used by [name] and her research group. Thirty hours of training will be conducted over 6 weeks. PLs will receive training in facilitation skills, coping strategies, and empowerment-based communication skills. As noted in Phase 1, training will be adapted to include a focus on men's health issues. Training will be group-based and include both the knowledge and skills needed to implement empowerment-based DSMS. A CDCES who was involved in the development and implementation of the training curriculum in previous projects, will conduct the training. This training will support the PLs in developing communication, facilitation, and behavior change skills and opportunities to apply those skills in an experimental setting. To ensure that PLs are supported, 3-monthly meetings will be held with all PLs so that they may exchange information and support each other. As noted above, it is expected that this content will be adapted to include men's health concerns based on Phase 1. PLs will be identified from interviews, based on recommendations from the senior center, and/or from the DataDirect participant pool. PLs will be compensated at \$10/ hour for the duration of the study to defray the cost of their time and expenses.

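### The serious-event window is undefined, the reference period for new events does not fit the 60 randomized men, and no event inquiry common to both arms is scheduled

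*Combined protocol and SAP*

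**What the plan says.** Section 9 (Data and Safety Monitoring Plan, Adverse Events) gives two windows. For adverse events in general: "The PI will monitor adverse events throughout the clinical trial period". For serious events: "Serious medical events will be collected throughout the intervention phase of the study".

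The same section opens its definition broadly: "adverse events will be considered any undesirable sign, symptom, or medical condition occurring during the study, whether or not related to the intervention". It then adds a reference period: "Adverse events include new events not present during the training period", together with events already present in that period that later became more severe. On recording, it says: "Each adverse event will be recorded and assessed for its date of onset, duration, severity, seriousness, and relationship to study treatment". Events go on an adverse event form, and field staff are to report them to the principal investigator at once.

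The only training described for participants is that of the peer leaders. Section 4.0: "Four of the participants will attend 30- hours of training and function as peer leaders during the intervention DSMES". Section 5.0 (Peer Leader Training): "Thirty hours of training will be conducted over 6 weeks".

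On contact, section 1.0 places six weekly education (DSME) classes in weeks 3-8, six weekly support (DSMS) sessions in weeks 9-14 and the post-treatment battery in weeks 15-16. Section 5.0 (Control Group) gives controls six DSME sessions and says "they will not receive any DSMS or ongoing support from PLs". Section 5.0 (Follow-Ups) brings both arms back for the post-treatment assessment.

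**The concern.** Three gaps in the plan bear on the same data.

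- **Window.** The one sentence that sets a collection period for serious events uses a narrower and undefined term than the sentence for all adverse events. Staff following it literally might stop asking about serious events when the sessions end.
- **Reference period.** Staff who must decide whether an event is new or has worsened are pointed to a period that the randomized men do not have.
- **Ascertainment.** The plan does not say when, how or by whom men in either arm are asked about events. If events come to light through contact, the arm with more contact will tend to show more of them.

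The Data Safety and Monitoring Board is charged in section 9 with monitoring interim safety data, including adverse events. Section 3.0 says the pilot will shape the protocol of a larger trial. With 30 men per arm, a few events captured in one arm and missed in the other could make the peer-led programme look less safe than it is.

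**Working it through.** The plan states no figure on this point to reproduce. The check compares the text and counts scheduled contact.

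**1. What the intervention phase could mean**

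| Place | Usage | Period implied |
|---|---|---|
| Section 1.0, on men who do not complete it | Set apart from the 3-month assessment | Sessions only, weeks 3-14 |
| Section 1.0, timing of the post-treatment battery | Weeks 15 and 16 counted as part of the intervention | Up to week 16 |
| Section 5.0, Data Collection & Data Safety | All of Phase II labelled as intervention | Baseline to last assessment |

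On the first reading, 16 - 12 = 4 weeks of the 16-week schedule (weeks 1-2 and 15-16) fall outside the serious-event window. On the third, nothing does. Sections 2.0, 7.0 (Specific Aim 2) and 10.0 refer to a follow-up after the post-treatment assessment, but section 5.0 schedules none. If that follow-up is real, serious events after week 16 fall outside the first two readings in both arms.

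**2. Who has a training period**

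Sections 4.0 and 7.0 give 64 participants, of whom 4 train as peer leaders. That leaves 64 - 4 = 60 randomized men with no training period.

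**3. Scheduled contact**

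Inputs are the session counts and weeks in sections 1.0 and 5.0, assuming the control DSME classes also run in weeks 3-8.

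- Sessions: intervention 6 + 6 = 12; control 6.
- Weeks with scheduled contact, counting baseline (weeks 1-2) and post-treatment assessment (weeks 15-16): intervention 2 + 12 + 2 = 16 of 16; control 2 + 6 + 2 = 10 of 16.
- Control gap: 16 - 10 = 6 weeks, namely weeks 9-14.

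**4. Possible effect on recorded events**

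These assumptions are not in the documents: the true event rate is equal and constant in both arms over weeks 3-14; events in weeks with a session are recorded; and a share r of control events in weeks 9-14 is recovered at T1. With 30 men per arm, the rate and the arm size cancel:

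recorded ratio, intervention:control = 12 / (6 + 6r)

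| r | Ratio |
|---|---|
| 0 | 12 / 6 = 2.0 |
| 0.5 | 12 / 9 = 1.33 |
| 1 | 12 / 12 = 1.0 |

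The ratio is 1.0 when every control event in the gap is recovered at T1. An event form at T1 is meant to move r towards 1.

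**The case against.** The strongest reply is that section 9 already covers the whole study. Its main definition takes in anything that occurs during the study, and every event is assessed for seriousness, so serious events are a subset of a study-wide collection. A reader might infer that serious events are collected only in the intervention phase, but the text does not say so. This reply stands against that reading. It does not remove the conflict between the two windows or define the phase.

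A reader might also infer that the training-period sentence excludes events, or that an event starting in the DSME weeks would count as pre-existing. The sentence says that adverse events *include* those new since training, after a study-wide definition, so it excludes nothing by itself. Nothing in the plan equates training with the DSME weeks. What remains is that the reference cannot be applied to the randomized men.

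A third tempting reading is that controls are not seen again once their classes end. They are: both arms attend the assessment in weeks 15-16. Some routes to events are also the same in both arms: the health services utilization questionnaire (section 7.0), and A1c and blood pressure measurements with alert values (section 9). None of these is an adverse-event inquiry, and the plan does not link them to the event form.

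Finally, the plan does not say that events are found at sessions. In weeks 9-14 the sessions are led by peer leaders, whom section 9 does not name among those trained to report events. If those sessions yield few reports, the arms would differ less. Section 8.0 describes the risks as minimal, and no between-arm safety comparison is planned. These points limit the size and weight of the concern. They do not supply the missing common inquiry.

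**Conclusion.** The concern holds as a conflict in the text and a risk of unequal capture. Three things are established from the documents: two unreconciled collection windows, one of them undefined; a reference period that applies to 4 of 64 participants and to none of the 60 randomized men; and 12 sessions against 6 with no scheduled inquiry about events common to both arms.

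The size of any imbalance is not established. The range of 1.0 to 2.0 rests on equal true rates, on events being found through contact, and on control classes running in weeks 3-8. A reader might infer that the plan produces a spurious doubling of events in the peer-led arm. The documents do not support that: 2.0 is the extreme at which no control event in weeks 9-14 is recovered at T1, and the plan gives no capture rates. The change is still worth making, because these gaps affect the safety data the monitoring board will see and the protocol carried into the larger trial.

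**What to change.** - Reconcile the two sentences in section 9 so that adverse and serious events are collected in both arms from consent to the last assessment. State which assessment is the last, given the mentions of later follow-up in sections 2.0, 7.0 and 10.0.
- Define new or worsened relative to the T0 baseline assessment, in place of the training period.
- Give the existing adverse event form to every man in both arms at T1, with the same questions covering the whole period since T0.
- Optionally, report events by how they were found (at a session or on the T1 form).

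The cost is protocol wording and a few minutes per participant at a visit already scheduled. Recall of minor events over that interval will be imperfect, but the question will be the same in both arms.
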